9.2. Pharmacokinetic Parameters Estimation

The PK parameters will be calculated by a dedicated CRO (

A population PK (popPK) model was developed using nemolizumab serum concentrations from 3 clinical studies conducted in adults (CIM001JP, CIM003JG, and SPR114322). The model developed in adult subjects will be used to derive empirical Bayes estimates in the adolescent population based on their baseline characteristics, their dosing history and their measured concentrations. The adequacy of the model to properly describe the adolescent data will be based on the model diagnostic tools described in a in dedicated PK modeling plan and report.

One interim PK analysis will be done with the available SPR116912 serum concentrations from the 10 first subjects up to the cut-off date corresponding to week 8. The interim PK analysis will be updated with final data when available and presented in the final report.

Estimates of main population PK parameters (CI/F, V_d/F, T_{lag}, k_a), including inter-individual variability, covariate effects, residual error and their relative standard error (RSE), will be obtained using the popPK model described above.

Other individual nemolizumab PK parameters (C_{max}, T_{max}, C_{trough 4w}, C_{trough 8w}, C_{trough 12w}, C_{trough 16w}, AUC_{0-4w}, AUC_{0-12w}, AUC_{0-16w}, AUC_{0-16w}, AUC_{inf} and t_{1/2}), will be derived using the same popPK model.

Some individual nemolizumab PK parameters (AUC_{0-4w}, AUC_{0-8w}, AUC_{0-12w}, and AUC_{0-16w}) will be also calculated using a non-compartmental analysis (NCA) using only the observed serum concentrations from study SPR116912.

Details about calculation of PK parameters (NCA and popPK) will be described in a separated PK modeling plan.

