# 6.2 Primary Endpoints

#### 6.2.1 Pharmacokinetics

- Nemolizumab serum concentrations at baseline, Weeks 1-2, 4, 8, 12, 16, 24 and unscheduled visits for safety reasons
- Nemolizumab serum PK parameters at steady state extrapolated with a population PK analysis (Cl/F, Vd/F, Tlag, ka, Cmax, Tmax, Ctrough, AUC0-4w, AUC0-8w, AUC0-12w, AUC0-16w, and t1/2)

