#### Notes:

- a Subjects are required to fast for at least 8 hours before the visit(s).
- b Visit 3 is a single visit occurring between Week 1 to Week 2.
- c For subjects that complete the Week 16 visit and will rollover to the nemolizumab LTE study, the Week 16 visit (Visit 7) will serve as the final study visit. See Section 7.6.1.
- A follow-up visit is required for subjects who discontinue after the Week 16 visit and will not rollover to the nemolizumab LTE study. The follow-up visit should occur 12 weeks after the last study drug injection. See Section 7.6.1.
- e Assessments to be conducted at the unscheduled visit(s) depend on the reason for the visit. See Section 7.6.2.
- Subjects who discontinue before the Week 16 visit should attend an early termination visit and a follow-up/final study visit 12 weeks after the last study drug injection. See Section 7.6.1.

CONFIDENTIAL Page 37 of 99

Galderma Research & Development, LLC Protocol Number: RD.06.SPR.116912 21-JUL-2020 Version 6.0

- g Patient-reported efficacy measurements (ACT and DLQI/cDLQI) should occur before investigator (efficacy and safety) assessments, blood sample collections, and study drug administration.
- h Peak and average pruritus NRS should be recorded by subjects once daily in the evening, beginning ≥ 2 weeks before Day 1.
- Sleep disturbance NRS should be recorded by subjects once daily in the morning, beginning ≥ 2 weeks before Day 1.
- Subjects will be asked to record the response (yes/no) to the following question each evening, "Did you apply the eczema medication your doctor gave you, to your skin today?", beginning ≥ 2 weeks before Day 1. See Section 7.5.8.1.1.
- Subjects with a history of asthma will complete the ACT at each study visit before physical examination and other investigator assessments. Subjects with de novo diagnosed asthma will complete the ACT beginning at the first visit of de novo diagnosis and at all follow-up study visits.
- Subjects aged 17 years or older will complete the DLQI, while subjects aged 12-16 years old will complete the cDLQI.

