The duration of the follow-up period (ie, 12 weeks after the last study drug administration), corresponds to 5 half-lives of nemolizumab: the drug plasma level is expected to be lower than the Limit of Quantification at the end of the study, and the follow-up period is therefore considered adequate to ensure the safety of subjects.

Background therapy including moisturizer and authorized TCS will be used throughout this study. This is in line with the current practice to use topical agents in conjunction with systemic treatment in more severe cases. Background TCS will be started from the screening visit, to ensure disease stability and avoid flares. The potency of TCS selected for this study is clinically justified. A medium potency TCS will be used on the body where considered safe (eg, trunk and extremities), and a low potency TCS will be used in TCS-sensitive areas (eg, face, neck, intertriginous areas). The prescribed background TCS use should be within daily frequency limits according to the product labeling. Background TCS use includes guidelines to adjust usage to disease activity and

CONFIDENTIAL Page 39 of 99

tolerability of the subject, including tapering when signs and symptoms improve, discontinuation when lesions clear, and restarting if signs and symptoms recur.

Rescue therapy including topical and systemic treatment or phototherapy may be provided if judged to be necessary by the investigator.

This study will assess the PK and safety profile of nemolizumab in the adolescent population, in order to allow their subsequent enrolment in planned Phase 3 studies.

Nemolizumab serum concentration will be assessed at baseline, Weeks 1-2, 4, 8, 12, 16 and Week 24 and at any unscheduled visit for safety reasons. Given that the nemolizumab drug supply configuration and preparation are similar to that used in the Phase 2b study involving adult AD subjects, no change is anticipated in the absorption phase (ka). Thus, limited PK assessment will be done during the absorption phase and serial pre-dose PK samples will be collected at steady state.

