#### 8.2.2 PK Parameters

PK parameters of nemolizumab in the serum will be calculated by the designated CRO using 2 analyses:

PK parameters will be derived using a non-linear mixed effect modeling approach with NONMEM. A pre-specified population PK model based on existing information from previous studies in adults (first-order absorption and a 1-compartment distribution model) will be used to derive empirical Bayes estimates in the adolescent population based on their baseline characteristics, their dosing history and their measured concentrations. The adequacy of the model to properly describe the adolescent data will be based on the model diagnostic tools described in a in a dedicated PK modeling plan. Estimates of main population PK parameters (Cl/F, Vd/F, Tlag, ka), including inter-individual variability, covariate effects, residual error and their relative standard error [RSE]), will be obtained using the popPK model.

- Other individual nemolizumab PK parameters will be derived using the same popPK model (Cmax, Tmax, Ctrough, AUC0-4w, AUC0-8w, AUC0-12w, AUC0-16w, and t1/2).
- In addition, a static analysis based on pre-dose (Ctrough) serum concentration will be
  performed using an NCA. Data from subjects with missing concentration values (missing
  samples) may be used if PK parameters can be estimated using the remaining data points.

For the NCA analysis, the following PK parameters will be determined for each subject based on Ctrough concentration:

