# 9.4.2 PK Parameters and ADA Analyses

The PK parameters obtained using modelling techniques will be regarded as primary endpoints for the PK analyses (see details in Section 6.4.1). Primary inference for all the PK parameters will be based on the pharmacokinetic analysis population.

The PKPD relationship between nemolizumab plasma concentrations and the selected clinical outcomes (EASI, IGA and NRS) will be investigated, as appropriate, using a PKPD model development based on previous clinical data.

The pop-PK and PKPD models will be detailed in a separate Modeling Analysis Plan.

The concentration at each time point will be summarized as arithmetic mean, standard deviation, median, minimum, and maximum, number of BLQs (Below the Limit of Quantification).

Descriptive statistics (n, arithmetic mean, standard deviation [SD], minimum, median, maximum) will be calculated for all PK parameters obtained using NCA.

For ADA analyses, the incidence of positive ADA results will be summarized (absolute occurrence, percent of subjects, treatment-related ADA). A presentation of ADA results will be detailed in the SAP.

CONFIDENTIAL Page 74 of 99

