8.8. Dermatology Life Quality Index

Dermatology Life Quality Index (DLQI) is a validated 10-item questionnaire for subjects aged > 16 years, covering domains including symptoms/feelings, daily activities, leisure, work/school, personal relationships and treatment. DLQI data will be recorded in the CRF. Children's DLQI (cDLQI) is a

comparable validated 10-item questionnaire designed for pediatric subjects and cDLQI will be used if the subjects are aged 16 years or less. Each question in DLQI/cDLQI has values in a range between 0 (not at all) and 3 (very much) as defined in Table 4:

Table 4: DLQI and cDLQI question point score

Score	DLQI	cDLQI
0	Not at all	Not at all
1	A little	Only a little
2	A lot	Quite a lot
3	Very much	Very much

The DLQI/cDLQI total score is calculated by summing the score of each question resulting in a maximum score of 30 and a minimum of 0. The higher the score, the more quality of life is impaired.

DLQI and cDLQI scores and their change from baseline will be summarized descriptively by visit as continuous variables.

All DLQI/cDLQI data will be listed.

No LOCF analysis will be performed for DLQI/cDLQI.

9. Pharmacokinetics/Pharmacodynamics

PK analyses will be performed using the PK Population. No missing data imputation will be performed.

The serum concentration of nemolizumab will be assessed at baseline, Weeks 1-2, 4, 8, 12, 16, 24 and at any unscheduled visit for safety reasons. At the study drug injection visits (baseline, Weeks 4, 8 and 12), PK samples will be collected within 30 minutes before study drug injection (pre-dose samples). At Weeks 1-2, 16 and 24, attempts should be made to collect PK samples at approximately the same time of the day, to the extent possible.

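### Adolescent Tlag, ka and Tmax are empirical Bayes estimates from an adult model with one sample near absorption, so near-adult values for them are not evidence of similarity

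*SAP*

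**What the plan says.** Protocol 8.2.2 specifies "A pre-specified population PK model based on existing information from previous studies in adults (first-order absorption and a 1-compartment distribution model"), and SAP 9.2 adds: "The model developed in adult subjects will be used to derive empirical Bayes estimates in the adolescent population". Protocol 6.2.1 lists Cl/F, Vd/F, Tlag, ka, Cmax, Tmax, Ctrough, AUCs and half-life at steady state as primary PK endpoints. Protocol 9.4.2 confirms the rank: "The PK parameters obtained using modelling techniques will be regarded as primary endpoints for the PK analyses". SAP 9.3 summarises the individual derived parameters with mean, SD, geometric mean, %CV and 95% CI.

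A second primary PK endpoint in Protocol 6.2.1 needs no model: "Nemolizumab serum concentrations at baseline, Weeks 1-2, 4, 8, 12, 16, 24 and unscheduled visits for safety reasons". The non-compartmental AUCs are secondary and use only this study's observations.

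On sampling, the notes to Protocol 7.2 say "Visit 3 is a single visit occurring between Week 1 to Week 2", scheduled at Day 10 ± 3. At the dosing visits, the opening text of SAP section 9 says "PK samples will be collected within 30 minutes before study drug injection (pre-dose samples"). Weeks 16 and 24 fall 4 and 12 weeks after the last dose, and Week 24 applies only to subjects who do not roll over. Protocol 7.3.1 gives the reason for the sparse early sampling: "no change is anticipated in the absorption phase (ka). Thus, limited PK assessment will be done during the absorption phase".

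Model adequacy is left to diagnostics in a separate PK modeling plan. Neither document requires shrinkage to be reported or sets a similarity criterion.

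**The concern.** An empirical Bayes estimate is a compromise between a subject's own data and the model's prediction for someone with that subject's covariates. Where the data say little, it stays near the prediction, and here the prediction comes from adults. The protocol assumes that ka is unchanged, uses that assumption to justify limited absorption sampling, and then lists ka, Tlag and Tmax as primary adolescent results. For those parameters the assumption comes back as a finding.

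The parameters are also described as steady-state values, yet the one scheduled sample inside a dosing interval follows the 60 mg loading dose. No scheduled sample lies inside a 30 mg interval, so steady-state Cmax and Tmax are model output.

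The trial asks whether adolescent PK resembles adult PK, as a basis for enrolling adolescents in Phase 3. Near-adult absorption parameters with tight intervals could be cited in support although the design could hardly have shown anything else.

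**Working it through.** The documents state no shrinkage, precision or power figure, so there is no plan figure to reproduce. The check asks how much adolescent information reaches each estimate.

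**Inputs from the documents.** One compartment with first-order absorption; 60 mg, then 30 mg at Weeks 4, 8 and 12; samples at Day 10 ± 3 and Weeks 4, 8, 12, 16 and 24 (final), or the first three (interim). Protocol 7.3.1 equates 12 weeks with 5 half-lives, so t½ = 84/5 = 16.8 days and ke = ln 2/16.8 = 0.041/day.

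**Inputs assumed because not given.** Adult ka 0.2 to 1.2/day; V/F 7 L; Tlag 0.25 day; between-subject SD on the log scale 0.30 (CL/F), 0.25 (V/F), 0.4-0.6 (ka) and 0.4 (Tlag); residual error 15-20%; no covariates; adult prior held fixed.

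**Step 1: what the early sample can see.** The fraction of the dose absorbed by time t is 1 − exp(−ka·t). At 10 days this is 86.5% for ka 0.2/day, 98.2% for 0.4 and above 99.9% for 0.8. Study Day 10 is strictly 9 days after a Day 1 dose, which gives 1 − exp(−1.8) = 83%, 1 − exp(−3.6) = 97% and 99.9%. Ignoring the lag, Tmax = ln(ka/ke)/(ka − ke) = 9.9, 6.3 and 3.9 days. Unless ka is low, the sample falls after the peak, when absorption is nearly over.

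**Step 2: simulated empirical Bayes estimates.** Shrinkage is 1 − SD(estimates)/ω, where ω is the between-subject SD. Recovery is the share of a true log-scale shift from the adult value that the estimates show.

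| Quantity | Final sampling | Interim sampling |
|---|---|---|
| Tlag shrinkage | 98-99% | 98-99% |
| ka shrinkage, adult ka 0.2 | 36-37% | 36-46% |
| ka shrinkage, adult ka 0.4 | 45-56% | 52-74% |
| ka shrinkage, adult ka 0.8 | 85-89% | 88-91% |
| 30% V/F shift recovered | 68-88% | 32-60% |
| Cmax recovery, CL/F and V/F both shifted 30% | 52-85% | 34-79% |
| AUC0-16w recovery, same joint shift | 70-88% | 69-90% |
| 30% CL/F shift recovered | 87-101% | 85-103% |

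The Week 16 trough is 89-96% recovered at the final analysis under the joint shift.

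**Step 3: direction of the absorption change (final sampling).**
- ka doubled: recovery is 20-21% at adult ka 0.2 and about 0% at 0.4 and above. At 0.4, median Tmax is 6.6 days in adults, truly 4.2 in adolescents, and estimated as 6.5.
- ka halved: recovery is 60-69% at 0.2, 38-58% at 0.4, and 8% or less at 0.8 and above. At 0.2, Tmax is 10.2 days in adults, truly 15.4, and estimated as 13.6.
- Tlag tripled: 0% recovered.

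**Step 4: effect on the planned intervals.** SD(estimates) = (1 − shrinkage) × ω. With n = 20 and ω = 0.4, the log-scale 95% half-width without shrinkage is 2.093 × 0.4/√20 = 0.187, roughly ±20%. At 98% shrinkage it becomes 0.02 × 0.187 = 0.004, about ±0.4%. For ka at 89% shrinkage it is 0.11 × 0.187 = 0.021, about ±2%. In that last setting (adult ka 0.8), a true doubling of ka would be missed.

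**The case against.** A reader might infer that similarity is built into the trial's conclusion, or that the interim decision rests on shrunken estimates. The documents do not support that. Protocol 7.1 and SAP section 13 frame the interim around observed safety and PK data. In the SAP index, concentration table 14.2.3.1 and figures 14.2.3.5 to 14.2.3.7 are marked for the interim, and popPK table 14.2.3.2 is not. SAP 9.2 does plan an interim PK analysis within the popPK section, so a modelled interim result is possible but is not shown to drive the decision.

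A reader might also infer that a clearance difference would be badly understated at the interim. That depends on assumed inputs. With residual error of 20-30% and both CL/F and V/F truly 0.68 of adult beyond the model's covariates, interim CL/F averages 0.75-0.80. With 15-20% error and a CL/F-only shift, 85-103% is recovered. Nothing in the documents points to a shift of either kind.

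Three further points have weight:
- The estimates use baseline characteristics, so shrinkage is toward a covariate-adjusted prediction, not one adult value.
- SAP 9.2 promises population parameters with relative standard errors but does not say whether they are re-estimated. The simulation assumes that they are fixed.
- Shrinkage reporting may sit in the modeling plan, which is not available here. Nothing in the protocol or SAP says that ka, Tlag or Tmax will be cited as similarity evidence, and the protocol is open about its ka assumption.

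These points limit the concern without removing it. The parameters are primary, they will be tabulated with CIs, and the non-compartmental analysis shares the sparse samples and yields no ka, Tlag, Cmax or Tmax.

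**Conclusion.** The concern holds for the absorption parameters. Tlag carries essentially no adolescent information. ka and Tmax carry little if absorption is faster than in adults, and a partial signal if it is slower and adult ka is low. Near-adult values are therefore uninformative about similarity, and CIs computed across shrunken estimates would be too narrow. V/F and Cmax are partly affected, most at the interim, where about 32-60% and 34-79% of a shift is recovered. CL/F and trough are mostly set by the adolescents' own samples, and AUC largely so.

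It would go too far to say that all the primary popPK parameters return adult values. It would also go too far to say that the method cannot show a difference. Cmax and slower absorption are partly recoverable, and observed concentrations and non-compartmental AUCs do not depend on the adult prior.

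The sizes rest on assumed adult ka, variability and residual error and on a fixed adult prior. They illustrate the mechanism and do not reproduce the sponsor's model. The change is worth making but does not put the trial in question.

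**What to change.** In SAP 9.2 and 9.3:

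1. Rest the adolescent-adult conclusion on observed concentrations. Support it with a joint fit of adult and adolescent data that estimates adolescent/adult ratios for CL/F and V/F with CIs. State that these ratios will be imprecise at the interim, with about 10 subjects. State also whether population parameters are held at adult values or re-estimated.
2. Report eta-shrinkage for each parameter beside its summary.
3. Label Tlag, ka and Tmax, and steady-state Cmax where shrinkage is high, as adult-model-derived, and do not use them as evidence of similarity.

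No extra visit or sample is needed. The cost is one additional model run, some SAP wording, and fewer parameters that can be claimed as adolescent findings.

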9.3. Pharmacokinetic Parameters Presentation

Estimates of main population PK parameters (Cl/F, Vd/F, Tlag, ka), including inter-individual variability, covariate effects, residual error and their relative standard error (RSE), will be presented in a dedicated PK report.

Individual derived PK parameters at steady state estimated with the popPK model and individual observed PK parameters at steady state calculated with the NCA will be summarized using the following statistics: n, arithmetic mean, standard deviation, geometric mean, %CV, median, minimum, maximum and 95% CI. This descriptive statistics will be calculated CCI.

In addition, the comparison of the average observed trough (C_{trough}) nemolizumab concentration between ADA+ samples and ADA- samples will be performed using ANOVA and the comparison results will be presented.

All PK parameters will be listed by subject.

9.4. Pharmacokinetic/Pharmacodynamic Analysis

The PK/PD analysis will be done by a dedicated CRO (Certara).

Individual predictions and empirical Bayes post-hoc estimates generated from the popPK model will be used to develop PK/PD models for the following pharmacodynamic (PD) endpoints: eczema area and severity index (EASI), investigator's global assessment of dermatitis severity (IGA), and weekly average peak pruritus numeric rating scale (PP-NRS). For each patient, the concentration time-course will be predicted up to the last PD assessment time based on individual Bayes post-hoc estimates of the PK parameters, and will be used as a driver in the PD models. The PK/PD models will be described in a separate PK modeling plan.

10. Safety

The population used for safety analyses will be the Safety Population. Safety will be assessed on the basis of adverse event (AE), adverse event of special interest (AESI), clinical laboratory data, ECG parameters, physical examinations, Asthma control test, respiratory and vital signs.

10.1. Extent of Exposure and Compliance

The extent of exposure (treatment duration, total dose administered, planned dose and treatment compliance percentage) will be summarized.

Treatment duration (in days) is calculated as follows:

[(date of last treatment – date of first treatment) + 1].

Treatment compliance will be summarized based on the treatment records and drug dispensation logs recorded in the CRF. The compliance percentage will be calculated as dose volume administered / planned dose volume *100, with the planned dose of 60 mg on Day 1, followed by injections of 30 mg every 4 weeks for 12 weeks. Once the dosing solution is prepared,1.0 mL of it will be drawn into a syringe, which will be administered subcutaneously in the abdomen of the subjects as planned dose.

Extent of exposure and treatment compliance will be presented in a listing for the Safety population.

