## 7.5.1 Investigational Product Administered

Nemolizumab drug supply configuration and preparation are similar to that used in the Phase 2b study involving adult AD subjects, to minimize exposure variability when comparing adolescent results to adults.

Nemolizumab will be supplied in single-use vials in the form of 153 mg lyophilized powder. The drug product is to be reconstituted by adding 1.3 mL of sterile water for injection. A vial of nemolizumab placebo will be used for dilution, to achieve desired dose level. (Syringes, needles, and sterile water for injection will be provided to the study centers for use in the trial.)

All study drug doses will be administered by trained and qualified personnel at study centers. Qualified personnel will prepare the dosing solution by mixing appropriate amounts of reconstituted nemolizumab, according to the provided "instruction(s) for use" in the pharmacy manual.

Table 6: Dosing Scheme

Group	Dose on Day 1	Dose at Weeks 4, 8, and 12
1	60 mg	30 mg

Once the dosing solution is prepared, 1.0 mL of it will be drawn into a syringe, which will be administered subcutaneously in the abdomen of the subjects. Other sites of injection may be permitted (ie, for safety reasons) after discussion with the medical monitor. The site of injection should be recorded in the subject's treatment record at each time point.

CONFIDENTIAL Page 47 of 99

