## 7.5.2 Identity of Investigational Product

Table 7: Description of Nemolizumab

Name	Nemolizumab
Internal code	CD14152
Pharmaceutical form	Lyophilized powder
Formula number	N/A
Packaging	Vial
Dosage	30 mg (with a loading dose of 60 mg at baseline)
Route	Subcutaneous injection
Dose regimen	Every 4 weeks (Q4W)
Treatment duration	16 weeks (last injection at Week 12)

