6.2. Key Definitions

The date of first treatment is defined as the date of first injection of nemoluzimab.

The date of last treatment is defined as the date of last injection of nemoluzimab.

Study day is defined as the number of days from the date of first treatment and will be calculated as follows:

- If the event date≥date of first treatment, study day = event date–date of first treatment+1.

 Treatment Day 1 is therefore defined as the day of first treatment.
- If the event date<date of first treatment, study day = event date-date of first treatment.

The baseline value will be taken as latest value prior to first injection of nemoluzimab. For subject enrolled but not treated, the baseline value will be the latest value prior to the treatment assignment.

A subject's date of last participation in the trial is the last date of contact and is recorded as the date of completion or date of withdrawal on the completion page of the CRF.

Treatment period is defined as the period between the date of first treatment.

- Up to the date of Week 16 for subjects who completed the treatment period
- Up to the earliest date between 4 weeks after the last study drug injection or the date of early termination for subjects discontinued the treatment period.

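### SAP exposure duration stops at the last injection (85 days of a 16-week treatment period), and compliance is measured by volume, so it may not reflect the mg given

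*SAP*

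**What the plan says.** SAP 10.1 summarises treatment duration, total dose administered, planned dose and a compliance percentage, and gives no unit for the two dose items in that list.

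**Duration.** The SAP says "Treatment duration (in days) is calculated as follows" and gives the expression "date of last treatment – date of first treatment) + 1". SAP 6.2 fixes both ends: "The date of first treatment is defined as the date of first injection of nemoluzimab" and "The date of last treatment is defined as the date of last injection of nemoluzimab".

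**Treatment period.** SAP 6.2 defines this separately. It ends at the Week 16 date for completers. For subjects who discontinue, it runs "Up to the earliest date between 4 weeks after the last study drug injection or the date of early termination". Protocol 7.5.2 (Table 7) describes the treatment duration as "16 weeks (last injection at Week 12".

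**Compliance.** "The compliance percentage will be calculated as dose volume administered / planned dose volume *100". The SAP then gives the plan in mg (60 mg once, then 30 mg) and describes 1.0 mL of prepared solution drawn into a syringe. Protocol 7.5.1 gives the same 1.0 mL and says how strength is set: "A vial of nemolizumab placebo will be used for dilution, to achieve desired dose level". Neither document says whether the 60 mg dose is one injection or two.

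**The concern.** Protocol 9.4.3.1 asks for the duration of exposure, and SAP 14 foresees no change from the protocol. A first-to-last-injection count leaves out the final 4-week dosing interval, which both Table 7 and SAP 6.2 treat as time on treatment. The study report would then carry two lengths of treatment: the SAP 6.2 period, used for rescue medication (SAP 7.6) and for selected laboratory and vital sign summaries (SAP 10.3, 10.4), and a shorter one in the exposure table.

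Compliance by volume is a sound measure only when volume tracks dose. Here the dose level is set by dilution on site, so a syringe of the right volume can hold the wrong amount of drug. In a study with PK in its primary objective, that is the dosing error one would most want the percentage to show.

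Both figures belong to Table 14.1.5.1, which SAP Section 18 marks for the interim analysis and for the IDMC.

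**Working it through.** **Duration**

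Inputs: first injection on Day 1; Week 12 injection on Day 85 ± 5 and Week 16 visit on Day 113 ± 5 (Protocol 7.2).

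- The protocol's figure: 16 weeks × 7 = 112 days. Day 1 to Day 113 is 112 elapsed days, or 113 counted inclusively. The SAP 6.2 treatment period therefore reproduces the 16 weeks.
- The SAP 10.1 formula: 85 − 1 + 1 = 85 days, or 12.1 weeks. Across the Week 12 window it gives 80 to 90 days.
- Shortfall: 112 − 85 = 27 days (27/112 = 24%). Counting both inclusively, 113 − 85 = 28 days (28/113 = 25%).
- One-dose subject: 1 − 1 + 1 = 1 day. The SAP 6.2 period gives up to 29 days inclusive (Day 1 to Day 29), or fewer if early termination comes sooner.

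Is the omitted interval exposed time? Protocol 7.3.1 equates 12 weeks with 5 half-lives, which implies 84/5 = 16.8 days. Assuming simple exponential decline, 2^(−28/16.8) = 0.31, so about 31% of the drug would remain 28 days later.

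**Compliance**

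Planned dose: 60 + 30 + 30 + 30 = 150 mg. Assuming one 1.0 mL injection per dosing visit, planned volume is 4 × 1.0 = 4.0 mL.

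| Case | By volume | By mg |
|---|---|---|
| All doses as planned | 4.0/4.0 = 100% | 150/150 = 100% |
| 30 mg in 1.0 mL on Day 1, rest as planned | 4.0/4.0 = 100% | 120/150 = 80% |
| 60 mg in 1.0 mL at all four visits | 4.0/4.0 = 100% | 240/150 = 160% |
| One 30 mg dose missed | 3.0/4.0 = 75% | 120/150 = 80% |
| Day 1 dose only | 1.0/4.0 = 25% | 60/150 = 40% |

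Each visit carries 25% of the volume, while the mg shares are 40% (60/150) for Day 1 and 20% (30/150) for each later dose.

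Alternative assumption: if the 60 mg dose were two 1.0 mL injections of 30 mg each, planned volume would be 5.0 mL. One missed 30 mg dose would give 4.0/5.0 = 80%, equal to the mg figure. The two measures would agree as long as each millilitre held 30 mg.

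**The case against.** First-to-last-dose duration is a recognised convention. The SAP applies it consistently and gives the longer treatment period its own name, and Table 7 of the protocol describes the regimen without defining an analysis variable. All of that stands, so this is not an arithmetic mistake. What remains is that the shorter count is reported as extent of exposure and disagrees with the plan's own account of time on treatment.

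A reader might infer three stronger things, which the documents do not support.

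- **Safety rates are distorted by about a quarter.** SAP 10.2 counts subjects and divides by the Safety population. No exposure-adjusted rate is planned, so no adverse event percentage changes.
- **The PK results are compromised.** The population PK analysis uses each subject's dosing history and measured concentrations (Protocol 8.2.2, SAP 9.2), not the compliance percentage.
- **A wrong-strength dose would go unseen.** Total dose administered is summarised beside the percentage, administration and dispensation are listed (16.2.5.1, 16.2.5.2), inadvertent dose modifications are to be reported (Protocol 7.5.7), and deviations are listed. The percentage by itself would not show the error, and total dose helps only if it is in mg, which is not stated.

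The equal-volume premise is also inferred. Preparation is left to a pharmacy manual outside these documents. In the notes to Protocol 7.2, the one on sample timing allows for more than one injection at a visit, while the one on observation ties the first two injections to the baseline and Week 4 visits, which points to one each.

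**Conclusion.** The point holds as a minor one. The duration part is certain: with dosing on the nominal days, the formula gives 85 days against 112 elapsed or 113 inclusive, a shortfall of 24 to 25%, and no injection day inside the Week 12 window closes the gap.

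The compliance part is conditional. If each dose is a single 1.0 mL injection, the percentage weights the 60 mg and 30 mg doses equally and reads 100% for any full-volume injection of the wrong strength. If the 60 mg dose is two 30 mg injections, the unequal weighting disappears.

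The effect is confined to the descriptive exposure and compliance figures in Table 14.1.5.1 and listings of the same values.

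**What to change.** Two edits to SAP 10.1:

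1. Define exposure duration as first injection to the end of the SAP 6.2 treatment period, counted inclusively: 113 days for an on-schedule completer, and for a discontinued subject to the earlier of 4 weeks after the last injection and early termination. If the first-to-last-injection count is still wanted, report it under its own label. SAP 6.2 names no end date for subjects still on treatment at the interim, so a cut-off date should be stated for them. Adding a flat 28 days to the last injection, capped at last participation, would create a third definition and is best avoided.
2. Compute compliance as total mg administered / planned mg × 100, with 150 mg as the denominator for four planned doses, and state mg as the unit of total and planned dose. Mg administered should come from the preparation and administration records; filling in the nominal dose would hide the same error.

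The cost is small: injection dates and planned doses are already specified and total dose is already to be summarised. No new data are needed, provided the treatment records show the mg in each injection. Dosing does not change.
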